#### 7.2.1 Definitions

##### **Evaluable for toxicity**

All patients will be evaluable for toxicity from the time of their first treatment with the study drug.

##### **Evaluable for objective response**

Only those patients who have measurable disease present at baseline, have received at least one cycle of therapy, and have had their disease re-evaluated will be considered evaluable for response. These patients will have their response classified according to the definitions stated below. (Note: Patients who exhibit objective PD prior to the end of Cycle 1 will also be considered evaluable.)

#### 7.2.2 Disease Parameters

##### **Measurable disease**

Measurable disease is defined as lesions (or tumors) that can be accurately measured in at least one dimension (longest diameter to be recorded) with a minimum size of 10mm by CT scan (irrespective of scanner type) and MRI (no less than double the slice thickness and a minimum of 10mm), 10mm caliper measurement by clinical exam (when superficial), and/or 20mm by chest X-ray (if clearly defined and surrounded by aerated lung).

All tumor measurements will be recorded in millimeters or decimal fractions of centimeters. Previously irradiated lesions are considered non-measurable except in cases of documented progression of the lesion since the completion of radiation therapy.

##### **Target lesions**

All measurable lesions, up to a maximum of 5 lesions total (and a maximum of two lesions per organ), representative of all involved organs should be identified as target lesions and recorded and measured at baseline. Target lesions will be selected on the basis of their size (lesions with the longest diameter) and their suitability for accurate repeated measurements (either by imaging techniques or clinically). A sum of the longest diameter (LD) for all target lesions will be calculated and reported as the baseline sum LD. The baseline sum LD will be used as reference by which to characterize the objective tumor response.

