##### **Non-measurable disease (Tumor Markers)**

Non-measurable disease is all other lesions (or sites of disease), including small lesions (longest diameter  $< 20$  mm with conventional techniques or  $< 10$  mm using spiral CT scan).

Leptomeningeal disease, ascites, pleural or pericardial effusion, inflammatory breast disease, lymphangitic involvement of skin or lung, abdominal masses/abdominal organomegaly identified by physical exam that is not measurable by reproducible imaging techniques are all non-measurable (e.g. PSA, CA-125, CA19-9, CEA).

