### 7.2.4 Response Criteria

#### **Evaluation of Target Lesions**

##### Complete Response

Disappearance of all target lesions, confirmed as permitted by observation on two separate observations conducted not less than 4 weeks apart. Any pathological lymph nodes (whether target or non-target) must have reduction in short axis to <10 mm (the sum may not be "0" if there are target nodes). There can be no appearance of new lesions.

By nature of neoadjuvant study design, responses will be unconfirmed in many patients in this study, as resection will often occur less than 4 weeks after scans.

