#### Evaluation of Best Overall Response

The best overall response is the best response recorded from the start of the treatment until PD/recurrence (taking as reference for PD the smallest measurements recorded since the treatment started) or surgical resection. The patient's best response assignment will depend on the achievement of both measurement and confirmation criteria.

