**Table 7.1 Response Criteria**

Target Lesions	Non-Target Lesions	New Lesions	Overall Response	Best Response for this Category Also Requires
CR	CR	No	CR	>4 weeks confirmation**
CR	Non-CR/ Non-PD	No	PR	>4 weeks confirmation**
PR	Non-PD	No	PR	
SD	Non-PD	No	SD	Documented at least once >4 weeks from baseline
PD	Any	Yes or No	PD	
Any	PD*	Yes or No	PD	No prior SD, PR or CR
Any	Any	Yes	PD	

\*In exceptional circumstances, unequivocal progression in non-target lesions may be accepted as PD

\*\*Due to neoadjuvant nature of this study, radiographic responses will often be unconfirmed due to surgical resection prior to repeat scans

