## 8.3 Analyses Plans

### 8.3.1 Analysis Population

All patients who receive a dose of osimertinib will be analyzed for safety and efficacy. Participants who discontinue from study participation prior to surgical resection may be replaced after discussion with the Study PI.

Demographic and baseline characteristics will be summarized. In general, frequency distribution and percentage will be used to summarize categorical measurements, while mean with standard deviation and median with interquartile range will be used to describe symmetric and skewed continuous measurements, respectively. Univariate analysis among variables will be assessed using the two-sample t-test, Wilcoxon-rank-sum test, or Chi-square test, as appropriate.

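### The radiographic response rules leave the ORR denominator, the measuring axis for nodes and the status of unconfirmed responses unsettled, so ORR and depth of response depend on choices the plan does not make

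*Combined protocol and SAP*

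**What the plan says.** **Who is counted.** Section 7.2.1 restricts response to patients with measurable disease at baseline who "have received at least one cycle of therapy, and have had their disease re-evaluated will be considered evaluable for response"; patients with objective progression before the end of cycle 1 are added back. Section 8.3.1 states: "All patients who receive a dose of osimertinib will be analyzed for safety and efficacy". Section 8.1.2 says the same. Section 8.3.3 defines ORR as best overall response up to surgery, with 95% confidence intervals and no denominator. It gives no population for depth of response (DpR).

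**How nodes are measured.** Section 7.1 uses only the largest diameter. Section 7.2.2 defines measurable disease by "at least one dimension (longest diameter to be recorded) with a minimum size of 10mm by CT scan (irrespective of scanner type") and then says: "A sum of the longest diameter (LD) for all target lesions will be calculated and reported as the baseline sum LD". Partial response (PR) and progression in Section 7.2.4 are changes in that sum. For CR, however, "Any pathological lymph nodes (whether target or non-target) must have reduction in short axis to <10 mm", and the non-target CR rule uses the same axis and limit. No baseline short axis is required.

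**Confirmation.** Section 7.2.4 says that the "best response assignment will depend on the achievement of both measurement and confirmation criteria". CR needs two observations at least four weeks apart. Table 7.1 asks for more than four weeks in both rows where the target lesions are in CR, and its footnote concedes that "radiographic responses will often be unconfirmed due to surgical resection prior to repeat scans".

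**Where the results are used.** DpR is a listed secondary endpoint (Section 2.4.2, Table 8.1) and enters Cox models in Section 8.3.3. ORR is planned in the Abstract and analysed in Section 8.3.3, but appears in neither list.

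**The concern.** Two analysts following the text could report different ORRs and different DpR values from the same scans. On the denominator, a patient stopped in cycle 1 by toxicity who becomes ineligible for surgery is a failure for major pathological response (MPR) under Section 8.3.2, but leaves ORR under Section 7.2.1. If that patient has no scan, the omission can only raise ORR. On nodes, response status and DpR turn on an axis the plan does not fix consistently. On confirmation, the plan keeps a requirement it expects many patients to fail and does not say how they are then classed. In an open-label single-arm trial of 27 patients, one reclassified patient moves ORR by 1/27 = 3.7 points, and the choice could be made after results are known.

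**Working it through.** **The plan's own figure.** No figure is stated for ORR or DpR. The only related design figure is 87% power for MPR (Section 8.1.1: 27 patients, 22% versus 50%, 5% level). An exact binomial test that rejects at 11 or more MPRs has P(X ≥ 11 | 0.22) = 0.0221 and P(X ≥ 11 | 0.50) = 0.876, which reproduces it. No radiographic quantity enters, so this point leaves it untouched.

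**1. Denominator.** Let k dosed patients stop in cycle 1 with no scan, and let 27 be dosed. Under Section 8.3.1, ORR = x/27; under Section 7.2.1, ORR = x/(27 − k). The ratio is 27/(27 − k) whatever the number of responders x. The documents give neither x nor k, so both are assumed:

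| Responders x | k | All dosed | Section 7.2.1 |
|---|---|---|---|
| 19 | 2 | 19/27 = 70.4% | 19/25 = 76.0% |
| 19 | 4 | 19/27 = 70.4% | 19/23 = 82.6% |
| 14 | 3 | 14/27 = 51.9% | 14/24 = 58.3% |
| 14 | 5 | 14/27 = 51.9% | 14/22 = 63.6% |

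For x = 14 the exact 95% intervals are 31.9 to 71.3% (n = 27), 36.6 to 77.9% (n = 24) and 40.7 to 82.8% (n = 22). With k = 0 the two rules agree.

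**2. Nodal axis.** Lesion sizes are assumed; the node is given as longest diameter × short axis.

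- Primary 30 to 20 mm, node 20 × 14 to 16 × 9 mm. Longest-diameter sum: 30 + 20 = 50 to 20 + 16 = 36, (36 − 50)/50 = −28.0%, stable disease (SD). With the node on short axis: 30 + 14 = 44 to 20 + 9 = 29, (29 − 44)/44 = −34.1%, PR.
- Primary 30 to 20 mm, node 25 × 16 to 22 × 9 mm. Longest-diameter sum: 55 to 42 = −23.6%, SD. With short axis: 46 to 29 = −37.0%, PR.

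In both, the node is below the 10 mm short-axis limit used for CR while its own longest diameter has fallen by only 20% (20 to 16) or 12% (25 to 22). DpR differs by 6.1 and 13.4 percentage points.

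**3. Confirmation against the schedule.** A one-cycle patient has one on-treatment scan (cycle 1 day 28) and surgery within 14 days of it (Sections 3.4 and 6.1.2.3), so a second scan 28 days later cannot precede surgery. A two-cycle patient skips that visit (Appendix 1, footnote 4) and is scanned at cycle 2 days 1 and 28, that is, study days 29 and 56: 56 − 29 = 27 days, or 21 to 33 with the ±3-day window at each visit. The nominal gap misses four weeks by a day.

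In Table 7.1 the row with target lesions in PR carries no confirmation requirement. A patient whose target lesions vanish also meets the 30% decrease that defines PR. On that reading, failed confirmation changes CR to PR and leaves ORR unchanged. DpR is a percentage change and needs no confirmation.

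**The case against.** Several stronger readings are tempting, and the documents do not support them.

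- **A reader might infer that any one patient could be CR, PR, SD or left out.** CR requires the target lesions to be gone, so a patient with a persisting primary, as in both examples above, is SD or PR only. A CR/SD conflict needs the primary to vanish. With a 12 mm primary going to 0 and a node going from 30 × 16 to 30 × 9 mm, the longest-diameter sum goes from 42 to 30 mm (−28.6%, SD) while the nodal clause for CR is met. That is an extreme invented case.
- **A reader might infer that the confirmation rule strips responders from ORR.** It mainly moves the CR/PR label. The CR rates in the Introduction run from 0.5% to below 2%, largely in advanced disease. Applied to 27 patients they give about 0.1 to 0.5 CRs.
- **A reader might infer that node-positive patients are misclassified.** The sums use longest diameter consistently, and such a sum can be applied beside a short-axis condition for CR. What stands is that the result depends on the axis, only in patients with nodal target lesions and chiefly near a threshold. The documents do not say how many there will be.
- **Section 7.2.1 may be the specific rule and Section 8.3.1 the general one.** That is a fair reading, but nothing says so, and Section 8.3.3 does not choose. The size of any increase rests on assumed early stops. A patient stopped in cycle 1 who was scanned and had responded would also be dropped, which lowers ORR.
- **The 10 mm and 20 mm size limits in Section 7.2.2 also clash,** but only for lesions of 10 to 19 mm on non-spiral technique. This is minor.

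**Conclusion.** The point holds as a lack of definition in secondary radiographic measures. The denominator conflict matters most: if 2 to 4 of 27 dosed patients stop in cycle 1 unscanned, Section 7.2.1 raises ORR by a factor of 27/25 = 1.08 to 27/23 = 1.17. The nodal conflict can move a patient between SD and PR and change DpR by several points, in patients with nodal targets only. The confirmation gap needs one clarifying sentence and has little effect on ORR. Responder counts, early stops and lesion sizes are all assumptions. Taking 27 as the dosed number is also a simplification, since Section 8.1.2 allows some replacement, though not of patients removed for treatment-related toxicity. MPR, N = 27 and the 87% power stand.

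**What to change.** - **Denominator.** In Sections 7.2.1 and 8.3.3, use all dosed patients for ORR, in line with Section 8.3.1. Count a patient with no post-baseline scan as a non-responder, and give the evaluable-only rate as a sensitivity figure. For DpR, analyse patients with a post-baseline scan and report how many lack one.
- **Nodes.** Use short axis for nodes and longest diameter for all other lesions, consistently in Section 7.1, in Section 7.2.2 (measurable disease, target and non-target lesions) and in the sums for PR, progression and SD in Section 7.2.4. Do not take a node with short axis below 10 mm as a target. Reword the CR definition so that disappearance applies to non-nodal targets. Changing Section 7.2.2 alone would leave Sections 7.1 and 7.2.4 in conflict with it.
- **Confirmation.** In the CR definition, the best-overall-response paragraph and Table 7.1, state that best response is unconfirmed up to surgery.
- **Tidying.** Remove the 20 mm limit for conventional techniques from the non-measurable disease paragraph.

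The cost is protocol wording, re-measurement of nodes on existing scans, and a reported ORR that may be slightly lower. No visit or treatment changes.

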##### **Non-target lesions**

All other lesions (or sites of disease) including any measurable lesions over and above the 5 target lesions should be identified as non-target lesions and should also be recorded at baseline. It is possible to record multiple non-target lesions involving the same organ as a single item on the case record form (e.g. “multiple enlarged pelvic lymph nodes” or “multiple liver metastases”). Bone lesions may be measurable if  $\geq 1$  cm on MRI. Measurements of these lesions are not required, but the presence or absence of each will be noted throughout follow-up.

##### **Non-measurable disease (Tumor Markers)**

Non-measurable disease is all other lesions (or sites of disease), including small lesions (longest diameter  $< 20$  mm with conventional techniques or  $< 10$  mm using spiral CT scan).

Leptomeningeal disease, ascites, pleural or pericardial effusion, inflammatory breast disease, lymphangitic involvement of skin or lung, abdominal masses/abdominal organomegaly identified by physical exam that is not measurable by reproducible imaging techniques are all non-measurable (e.g. PSA, CA-125, CA19-9, CEA).

### 7.2.3 Methods for Evaluation of Measurable Disease

All measurements will be taken and recorded in metric notation using a ruler or calipers. All baseline evaluations will be performed as closely as possible to the beginning of treatment and never more than 28 days before the beginning of the treatment.

The same method of assessment and the same technique will be used to characterize each identified and reported lesion at baseline and during follow-up. Imaging-based evaluation is preferred to evaluation by clinical examination when both methods have been used to assess the antitumor effect of a treatment.

#### **Conventional CT and MRI**

CTs should be performed with cuts of 10 mm or less in slice thickness contiguously.

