**3.3.1 Inclusion Criteria**

1. Males and females ≥18 years of age.
2. Histologically or cytologically confirmed NSCLC, performed on a biopsy that occurred within the last 90 days. This biopsy can be deferred if the procedure is deemed to represent an unacceptable safety risk to the patient by the Principal Investigator and as long as the patient has a prior biopsy showing non-small cell lung cancer.
3. Documented activating EGFR mutation (Exon 19 deletion, T790M, or L858R) on tumor samples by Clinical Laboratory Improvement Amendments (CLIA)-approved test.
4. Patients treated with osimertinib or another EGFR TKI (including erlotinib, afatinib, gefitinib, & rociletinib) are eligible if they received no more than 28 days of treatment, and if there is no evidence of grade 2 or greater treatment adverse events possibly related to treatment with the EGFR TKI.
5. PET-CT (computerized tomography) within the last 60 days showing radiographic stage I to IIIa lung cancer (mediastinal staging biopsy is allowed but not required).
6. Brain magnetic resonance imaging (MRI) (or CT if contraindication to MRI) within the last 60 days showing no evidence of metastatic disease.
7. Documentation that the patient is a candidate for surgical resection of their lung cancer by an American Board of Thoracic Surgery certified surgeon.

8. The patient must have a tumor size  $\geq 1$  cm in its longest diameter.
9. Eastern Cooperative Oncology Group (ECOG) performance status of 0-1.
10. Any unresolved toxicities from prior therapy greater than CTCAE grade 1 at the time of starting study treatment, with the exception of alopecia and grade 2 prior platinum-therapy-related neuropathy is allowed
11. Adequate organ function:
  - Hepatic Function:
    - Aspartate aminotransferase (AST) and alanine aminotransferase (ALT)  $\leq 2.5$   $\times$  upper limit of normal (ULN).
    - Bilirubin  $\leq 1.5 \times$  ULN, (Patients with documented Gilbert's syndrome and conjugated bilirubin within the normal range may be allowed into the study. In this event, it will be documented that the patient was eligible based on conjugated bilirubin levels).
  - Electrolytes: Potassium, magnesium, and calcium within normal range, patients may receive supplements to meet this requirement.
  - Hematologic Function:
    - Leukocytes  $> 3,000/\text{mCL}$
    - Hemoglobin (Hgb)  $\geq 9$  g/dL, with no blood transfusions in the 28 days prior to study entry
    - Absolute neutrophil count  $> 1,500/\text{mCL}$

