##### Progressive Disease

At least a 20% increase in the sum of the SLD of target lesions, taking as reference the smallest SLD recorded since the treatment started and minimum 5 mm increase over the nadir, or the appearance of one or more new lesions.

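### CT cuts may be as thick as the smallest eligible tumor, so the plan does not ensure reliable radiographic measurement of tumors of about 10 to 13 mm

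*Combined protocol and SAP*

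**What the plan says.** - **Slice thickness** (protocol Section 7.2.3, Conventional CT and MRI): "CTs should be performed with cuts of 10 mm or less in slice thickness contiguously".
- **Entry** (Section 3.3.1, criterion 8): "The patient must have a tumor size $\geq 1$ cm in its longest diameter". The imaging method for this measurement is not named.
- **Measurable disease** (Section 7.2.2): on CT, a "minimum size of 10mm by CT scan (irrespective of scanner type"), with no link to slice thickness. For MRI the same sentence adds a link: "MRI (no less than double the slice thickness and a minimum of 10mm").
- **Non-measurable disease** (Section 7.2.2): this includes "small lesions (longest diameter $< 20$ mm with conventional techniques or $< 10$ mm using spiral CT scan").
- **Who counts for response** (Section 7.2.1): "Only those patients who have measurable disease present at baseline, have received at least one cycle of therapy", with disease re-evaluated afterwards. Patients who progress before the end of Cycle 1 also count.
- **Response thresholds** (Section 7.2.4): partial response is a 30% fall in the sum of diameters. Progression is a 20% rise with a "minimum 5 mm increase over the nadir", or new lesions.
- **Consistency** (Section 7.2.3): each lesion is to be followed with one method and technique from baseline onward.

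CT supplies the decrease in maximum diameter and depth of response (Sections 2.4.2 and 8.3.3), the objective response rate (Section 8.3.3) and the progression check before Cycle 2 (Section 3.4).

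**The concern.** The slice limit was not matched to the tumor size that the trial admits. At the permitted extreme a 10 mm tumor is imaged on 10 mm slices. Each slice then averages tumor with surrounding lung, and the diameter read depends on where the slice boundaries happen to fall. The protocol recognizes this for MRI, through the twice-the-slice rule, but not for CT.

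The two parts of Section 7.2.2 also pull apart. A 12 mm tumor is measurable under the first part whatever the scanner. Under the second part it may be non-measurable if the scan counts as a conventional technique, a term that also heads the slice-thickness rule. That choice decides whether the patient enters the response analysis at all.

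Stage I disease is eligible, so small tumors are in scope, and a single target lesion offers no averaging across lesions. In 27 patients one reclassified response moves the response rate by 1/27 = 3.7 percentage points. Section 7.2.4 accepts that many responses will be unconfirmed because surgery follows soon after the scan, so a misreading will often not be caught by a repeat scan.

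**Working it through.** No figure stated in the plan depends on slice thickness, so there is none to reproduce. The check compares the limits and then uses a simple geometric model.

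**Step 1. Ratio of lesion to slice at the permitted limits.**
- CT: 10 mm / 10 mm = 1.
- MRI rule in Section 7.2.2: at least 2.
- Carried over to CT (an assumption, since the plan does not do this), a ratio of 2 requires 20 mm lesions at 10 mm cuts, or 5 mm cuts for 10 mm lesions.

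**Step 2. Model (assumptions, not from the documents).** The tumor is a single solid sphere of radius R = D/2 with uniform contrast. Slices are contiguous, of thickness T, at random position. An edge is read where tumor fills at least 50% of the slice, and the largest in-plane diameter is taken. Let c be the distance from the sphere's center to the center of the nearest slice, uniform on 0 to T/2. The reading is

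d = 2 × √(R² − m²), where m is the larger of c and T/4.

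**Step 3. Range of readings for a true 10 mm tumor (R² = 25).**
- T = 10: the maximum is 2√(25 − 6.25) = 8.7 mm and the minimum is 2√(25 − 25) = 0 mm.
- T = 5: the maximum is 2√(25 − 1.5625) = 9.7 mm and the minimum is 2√(25 − 6.25) = 8.7 mm.

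**Step 4. Does the tumor read as measurable (d at least 10 mm)?** This needs m ≤ √(R² − 25).
- T = 10: never, if R² < 25 + 6.25, that is D < 11.18 mm. Always, if R² ≥ 25 + 25, that is D ≥ 14.14 mm. At 12 mm the share is √11 / 5 = 66%, so 34% are missed. At 13 mm it is √17.25 / 5 = 83%.
- T = 5: never, if R² < 25 + 1.5625, that is D < 10.31 mm. Always, if R² ≥ 25 + 6.25, that is D ≥ 11.18 mm.

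**Step 5. False 30% decrease in an unchanged tumor, given a measurable baseline, T = 10.**
- 12 mm (R² = 36): the highest baseline reading is 2√(36 − 6.25) = 10.91 mm, reached when c ≤ 2.5. The 30% threshold is then 7.64 mm, which follow-up meets if c ≥ √(36 − 3.82²) = 4.63, with probability (5 − 4.63)/5 = 7.4%. At the lowest qualifying baseline, 10 mm, the probability is (5 − √(36 − 12.25))/5 = 2.5%. The highest reading makes up 2.5/3.32 = 75% of measurable baselines, and the rest average about 5.0%. Overall: 0.75 × 7.4% + 0.25 × 5.0% = about 6.8%.
- 13 mm (R² = 42.25): the highest reading is 12.0 mm and the threshold 8.4 mm. Follow-up needs c ≥ √(42.25 − 17.64) = 4.96, with probability 0.8%. Averaged over baselines this is about 0.5%.
- 14 mm: the lowest reading is 9.8 mm, above 0.7 × 13.08 = 9.2 mm, so the rate is 0.

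**Step 6. False progression, T = 10.** A tumor must be at least 11.18 mm ever to read as measurable. At that size the full spread is 10.0 − 5.0 = 5.0 mm, and it narrows as D grows (10.91 − 6.64 = 4.27 mm at 12 mm). The 5 mm increase is therefore not reached, even against a falsely low nadir.

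**Step 7. T = 5.** The largest apparent fall in an unchanged 10 mm tumor is 1 − 8.66/9.68 = 10.5%, and it is less in larger tumors. There are no false responses.

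**The case against.** The strongest reply is that 10 mm is a ceiling. Sites using thinner cuts comply already, and in the same model 7.5 mm cuts give no false response at any size from 10 to 20 mm. The problem needs both cuts near the ceiling and a tumor near the entry limit. This stands, and it rules out the reading that the smallest tumors cannot be measured.

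A reader might also infer that an unchanged 10 mm tumor on 10 mm cuts would be called a response in about 15% of scan pairs and a progression in about 4%. The model gives such rates only if the baseline requirement is ignored. That tumor reads at most 8.7 mm, so it cannot be a target lesion under Section 7.2.2. For it the problem is lost evaluability, not a false response. Only the decrease in maximum diameter carries no stated measurability condition, so noise in the smallest tumors could enter there.

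Two further replies carry less weight. The consistency rule in Section 7.2.3 does not name slice thickness and cannot fix slice position, and the model already uses equal thickness at both scans. The 20 mm cut-off for conventional techniques would supply the missing ratio for 10 mm cuts, but the other part of Section 7.2.2 sets 10 mm for every scanner type. The two cannot both be followed without a rule saying which applies.

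Finally, 5 mm cuts do not fully rescue a tumor of exactly 10 mm, which still reads 8.7 to 9.7 mm. That is correct.

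**Conclusion.** The concern holds in limited form. The plan permits CT slices as thick as the smallest tumor it admits and calls measurable, and its own cut-offs disagree. It therefore does not ensure reliable measurement of tumors of about 10 to 13 mm. At 10 mm cuts the larger effect is loss of evaluable patients: all tumors of 10 to 11 mm and about a third at 12 mm. False responses are the smaller effect, at about 6 to 7% of scan pairs at 12 mm and under 1% at 13 mm, with no false progression.

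These rates rest on an idealized sphere, a 50% edge rule and random slice position, and are illustrative. The documents give neither the tumor-size distribution nor the slice thickness that sites use, so the number exposed could be anywhere from 0 to all 27. The reach is limited to the decrease in maximum diameter, depth of response, objective response rate and the RECIST check before Cycle 2. The primary endpoint, major pathological response, is read histologically, and neither it nor the sample size in Section 8.1.1 is affected.

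**What to change.** In Section 7.2.3, require a contiguous CT slice or reconstruction thickness of 5 mm or less, the same at baseline and at every response scan within a patient. This meets the protocol's own twice-the-slice ratio at the 10 mm entry limit. Reconcile the two measurability cut-offs in Section 7.2.2 with it, so that one rule decides whether a tumor of 10 to under 20 mm counts. Because a tumor at the limit can still read slightly under 10 mm, also state how an eligible patient without measurable disease on the baseline CT is handled in each radiographic endpoint.

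The cost is a sentence or two in Section 7 and the matching imaging instructions. Sites that use thick reconstructions must change a setting. No extra scans are needed.
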